#### Information and communication technologies (ICT) and chronic disease management

The previously mentioned risks and challenges of chronic conditions can be addressed by ICTsupported self-management interventions using various delivery modes (automated functions for e.g. information delivery or symptom monitoring, communicative functions for access to (peer-to-peer) advice or supplementary modes like email, telephone or short messages) (Webb , Joseph, Yardley, Michie, 2010). ICT-based interventions are considered relevant for educating and empowering people living with chronic disease (17,18). If well-designed meaning that interventions included are effective and developed on a user-centred design, such interventions can have a true added value for chronic disease management. The cost effectiveness is a factor that needs also to be tested in addition to clinical effectiveness. If proven to be effective and user-friendly for end-users also including healthcare professionals, they have a potential for scalability and may reduce healthcare spending while improving access to care, patient outcomes and quality of life (Oldenburg, Taylor, O'Neil, Cocker & Cameron, 2015; Stellefson, Alber, Wang, Eddy , Chaney & Chaney, 2015; Gaikwad & Warren, 2009).

Based on the current evidence, ICT-based healthcare interventions have small to moderate effects on health-related behaviour of chronically ill older adults and the potential to improve their quality of life (Eland-de Kok, van Os-Medendorp, Vergouwe-Meijer, Bruijnzeel-Koomen

& Ros, 2011; Macea, Gajos, Daglia Calil & Fregni, 2010; Hamine, Gerth-Guyette, Faulx, Green & Ginsburg, 2015). Webb et al. (2010) found that, on average, interventions using the internet to promote behaviour change had a statistically small but significant effect on health-related behaviour (d(+) = 0.16, 95% CI 0.09 to 0.23). Several benefits of ICT-based interventions for people living with chronic conditions have been reported, such as a significant positive effect on knowledge (SMD 0.46; 95% confidence interval (CI) 0.22 to 0.69), social support (SMD 0.35; 95% CI 0.18 to 0.52) and clinical outcomes (SMD 0.18; 95% CI 0.01 to 0.35) (23). A significant positive effect on continuous behavioural outcomes (SMD0.20; 95%CI 0.01 to 0.40) has also been found (ibid.).

#### Usability – technology acceptance by older adults

Various factors have been identified that may influence the acceptance, (non-)usage and adherence to ICT-based healthcare interventions by community-dwelling older adults and their informal caregivers (Peek et al., 2014). Personality-based, social and clinical characteristics may positively or negatively affect the ICT-use of older adults, in particular their familiarity with modern electronic technology, age or socio-economic status (Walczuch, Lemmink & Streukens, 2007). For instance, one study identified regular users of a web portal for patients living with type 1 and 2 diabetes mellitus as higher educated and younger than non-users (Ronda, Dijkhorst-Oei & Rutten, 2014). However, other studies found no age-, gender- or gravity-of-disease-related determinants of adherence to ICT-based interventions with a general higher acceptance amongst more self-determined patients and those with a desire to age in place, meaning to live independently at home for as long as possible (Peek et al., 2014; Prescher et al., 2014; Feil, Glasgow, Boles & McKay, 2000). Whether or not eHealth interventions are used by community-dwelling older adults also depends on their concerns regarding technology, for instance related to high cost, privacy or security implications (Stevenson, Lloyd, Harrington & Wallace, 2013; Pyper, Amery, Watson & Crook, 2004). In addition, personality traits of individuals such as optimism, innovativeness, discomfort and insecurity play a significant role in predicting technology acceptance (Walczuch et al., 2007; Lam, Chiang & Parasuraman, 2008).

The success of ICT-based healthcare interventions also depends on whether intended users find them useful (Peek et al., 2014; De Vito Dabbs et al., 2009). *Usability* is defined as the measure of the ease with which a system can be learned and used, including its safety, effectiveness and efficiency (Preece et al., 1994). In terms of the usability of ICT-based healthcare interventions, older adults express e.g. problems related to functionality and practicability (poor design, navigation or unmet expectations), physical challenges to using eHealth and tele-monitoring solutions, low ease of use or lack of perceived benefit including poor integration with daily routines (Oldenburg et al., 2015; Ronda et al., 2014; Greenhalgh,

<sup>1 Recent findings on digital health literacy in Europe indicate that more and more Europeans tend to use the Internet and online resources to manage their health. Yet, it also indicates a digital divide with a substantial group of Europeans having no or little access to online resources. Amongst those citizens open to the Internet and use of ICT, the majority (59% of 26'566 respondents in the Flash Eurobarometer 404) goes online to search for healthrelated information; of those who do, 63% are in good state of health compared to only 37% of Europeans in a poor state of health (57). Similar findings exist in North America, even though there, six out of ten older adults aged 65 plus go online daily (35) whereas currently about one third of Europeans aged 55 years or older use the Internet every day (57). On both continents, two sets of user groups amongst older adults have been identified: those with relatively substantial technology assets (younger, highly educated, better income and health status) compared to those largely disconnected (older, less affluent, significant health challenges or disability) (ibid.).

Hinder, Stramer, Bratan & Russell, 2010; Smith, 2014; Nijland, van Gemert-Pijnen, Kelders, Brandenburg & Seydel ER, 2011; Jimison et al., 2008).

If eHealth interventions do not align closely with end-users attitudes, self-management practices and information needs, there can be a substantial risk that they will not be adopted or adhered nor be sustainable over time as users stop using the technology (Greenhalgh et al., 2010; Jimison et al., 2008). Expectations and opinions towards ICT-based chronic disease management solutions may also change when older adults actively use them and, thus, may fluctuate over time (Peek et al., 2014 ; Ronda et al., 2014). A user centred design in ICT development is therefore the state of the art to guarantee a successful use and implementation in different contexts. Optimally, usability needs to be established before testing the effectiveness and will be an important driver in future scalability of ICT solutions (De Vito Dabbs et al., 2009).

### SENACA – from web platform to self-management support system for older adults and informal caregivers

In Switzerland, an ICT-supported intervention consisting of a web platform for active health promotion and disease prevention for older adults has been developed including standardised tools for calculating chronic disease risk and evidence-based health information to increase health literacy. The development of this senior health academy (SENACA, www.senaca.ch) was originally funded by the Swiss State Secretary for Education, Research and Innovation and conducted in close collaboration with health professionals, behavioural scientists and ICT experts. Run by an independent SME (small and medium-sized enterprise) it has now evolved to the SENACA platform. It is a structured self-management support system and complex intervention with several interacting components (Craig et al., 2008), combining tele-monitoring devices and a solution for personalised health plans. In 2014, a limited feasibility pilot of the SENACA prototype has been conducted demonstrating its technological readiness for further testing and implementation. In addition, selected clients of a major Swiss pharmacy and health service provider have used the prototype. Their feedback suggests that it may have added value for chronic disease management and risk prevention.

SENACA's *usability*, the *behaviour change techniques* it builds on, *modes of delivery* and its *effects on health-related behaviour, clinical and QOL outcomes* need to be established in a larger group of end-users. Testing the usability of SENACA and practical effectiveness of this complex intervention is the goal of the multi-national EU-funded ambient assisted living (AAL) project USECARE. A consortium of three countries (Israel, Norway and Switzerland) will implement the enhanced SENACA prototype and will run a field test with older community-dwelling adults living with chronic conditions (i.e. diabetes, COPD, chronic heart failure) and informal caregivers. Findings from the study embedded in USECARE AAL will inform the prototype's future improvement and scalability process.

Key element of USECARE AAL is a multinational field-test of the enhanced SENACA prototype including a pilot-like study with two parts described in the following:

<sup>2 Another feasibility round on the enhanced version of the SENACA prototype is scheduled for Spring 2016.

<sup>3 For further information see www.usecare.eu for details (accessed April 2015).

<sup>4 These include, for instance, an estimate of SENACA's macro-economic potential and the development of a sustainable business plan.

**Part I – preliminary studies** on usability of SENACA from the perspective of community-dwelling older adults as well as their informal caregivers (mixed methods) and on mapping the prototype's behaviour change components and intervention characteristics.

**Part II** – to explore outcomes of SENACA by using a **pre-experimental design** to observe the evolution of a number of parameters during the implementation period of the prototype.

#### 2.1.1 Study objectives

By introducing the enhanced SENACA prototype to community-dwelling older adults with one or more chronic conditions as well as their informal caregivers, the **objectives** for the two pilot-like study parts are as follows:

#### Part I – Preliminary studies:

- a. To test the usability from community-dwelling, chronically ill older adults' and informal caregivers' perspective in using the SENACA prototype in everyday life (including the evaluation of a number of process parameters related to the use of prototype)
- b. To analyse and map the SENACA prototype as a complex self-management intervention from a technological, educational and behavioural perspective using established frameworks and taxonomies (e. g. Michie et al., 2013).

#### Part II – Pre-experimental design:

To explore the evolution of outcome parameters (clinical, behavioural and quality of life) deemed to be responsive to the SENACA prototype over time from baseline until end of data collection

#### Outcomes studied will be

#### as of aim la preliminary studies (usability):

- usability (intention to use, perceived ease of use, perceived usefulness)
- technology experience, preference in using technology
- errors (number and type of technical problems occurring)
- user satisfaction (actual use of technology [one time baseline], relative frequency of module use of SENACA prototype, adherence to SENACA program: initiation, implementation, discontinuation [time to event])

#### as of aim II pre-experimental design (evolution of outcome parameters):

- HbA1c, cholesterol, weight, BMI (clinical)
- physical activity, nutrition behaviour, smoking
- health-related quality of life (QoL)
- empowerment (e.g. self-efficacy and social support) and health behaviour process outcomes

The study findings and analyses combined will provide an insight into the end-user perception, usage patterns and potential added value of the enhanced SENACA prototype for chronic disease management and empowerment of community-dwelling older adults living with chronic conditions and informal caregivers. The findings will also help to identify how SENACA as a complex intervention works and what are its active ingredients. Insights from this study may fuel the development of estimates and calculations about SENACA's potential in decreasing burden of care and healthcare cost. Finally, exploring both acceptance and outcomes of SENACA may help to collect experiences on the research design and measurements used in the three countries, which may provide additional insight on how to test complex interventions like SENACA and be used as a stepping-stone for a potential future investigation on the effectiveness of the prototype.

#### 2.2 Methods

#### 2.2.1 Design

This multi-national and multi-centred mixed-methods study includes two parts:

- I) preliminary studies on usability and analysis of the prototype from technological, educational and behavioural perspective (taxonomy-guided)
- II) the use of a pre-experimental design. USECARE AAL is characterized by an existing complex intervention as well as funding for field-testing SENACA with a relatively small number of participants in three countries. Given the existing resources and limited timeframe of the project, there will be hardly any control over the sample formation as the USECARE AAL participants can neither be chosen by chance nor will they be representative of a certain population. However, the SENACA field-test is considered an opportunity for exploratory purposes on technology acceptance and various outcomes of the prototype. It is considered a cost-effective way to discern whether the potential exploratory findings are worthy of further investigation under more carefully controlled circumstances (Marguis, Larivée, Saey, Dubois & Tousignant, 2015). Thus, a pre-experimental design with a one-group pre-test post-test approach using a repeated post-test has been considered adequate for the exploratory purposes of USECARE AAL (Creswell, 2009; Campbell & Stanley, 1963; Shadish, Cook & Campbell, 2002). This design makes it possible to observe a number of parameters over time using repeated measures and mixed methods (QUAN-qual) during the implementation of the enhanced SENACA prototype (Figure 1). This appears to be the way forward when researching in natural situations where there is a low level of control over context factors and the formation of sample, which both could affect the outcome. While being a reasonable research design for the USECARE AAL purpose, there will be clear limitations because of the pre-experimental character, i.e. that the internal and external validity is low, hypothesis testing is not possible and generalizing results should be avoided.

<sup>5 The QUAN-qual model stands for an explanatory mixed methods design where quantitative data are collected first and are more heavily weighted (41).

#### Figure 1.USECARE AAL study design

#### 2.2.2 Settings and sampling

Recruitment for the study takes place in healthcare organisations in the three participating countries – Israel (IL), Norway (NO) and Switzerland (CH) – where the SENACA prototype is implemented in private homes of community-dwelling older adults with chronic conditions. Members of the USECARE consortium along with affiliate healthcare organisations are involved for field access (predominantly healthcare providers like hospitals and / or out-patient clinics, see table 1 for details).

Organisation (in alphabetical order)	Role in study
Assuta Medical Center, Tel Aviv (IL)	Co-Investigator, Clinical Assessment
Institute of Nursing Science, University of Basel; Careum Research, Zurich (CH)	Investigator, Clinical Assessment
Joint Research Centre, Institute for Health and Consumer Protection, Behavioural Economics Team, Ispra (IT)	Analysis of Behavioural Economics
Medical Network EMN, Kilchberg (CH)	Provider of intervention (SENACA prototype)
Open University of Catalunia, Barcelona (ES)	Analysis of Behavioural Economics
University Hospital North Norway, Norwegian Centre for Integrated Care and Telemedicine, Tromsoe (NO)	Co-Investigator, Clinical Assessment
University Hospital Zurich, Department of Internal Medicine, Center of Competence Multimorbidity, Zurich (CH)	Co-Investigator, Clinical Assessment
University of Oslo, Dept. of Health Management and Health Economics, Oslo, Norway (NO)	Co-Investigator, Clinical Assessment

#### Table 1. Role of involved organizations in USECARE study

#### Participants

Participants in the study are community-dwelling older adults aged 50 years and older living with one or more chronic diseases who are at risk of developing complications and/or destabilization of their chronic conditions (primary end-users) and their informal caregivers (secondary end-users, i.e. spouses, children or other non-family and family members). Study participants are recruited from healthcare organizations in the countries participating in USECARE AAL. Table 2 lists the *inclusion and exclusion criteria*, which are straightforward:

Table 2. Inclusion and exclusion of	criteria for USECARE AAL study.
-------------------------------------	---------------------------------

Community-dwelling older adults (primary end-users)				
Inclusion criteria	
 
receive medical care for one or more of the following chronic diseases in hospital settings and outpatient clinics: 
 
Chronic Heart Failure (CHF, New York Heart Association NYHA II-IIIa);
 
Diabetes Mellitus (DM, 6< HbA1c<9),
 
Chronic Obstructive Pulmonary Disease (COPD, GOLD I-II)
 
Special Orthopaedic Co-Morbidity (SOCM, after elective hip or knee replacement, health status temporarily destabilized respectively challenged, increased monitoring and formal/informal care)
 
having support of an informal caregiver that is aged 18 years or older
 
are aged 50 years and older (community-dwelling older adults, primary end-user)
 
 
 
			
Exclusion criteria	
 
known illiteracy (reading and writing difficulties)
 
lack of local language proficiency
 
lack of internet access
 
current major mental illness of moderate to severe level
 
major acute illness or surgery in past 3 months (except elective hip / knee surgery for patients with SOCM)
 
participation in another intervention study
 
			
Informal caregivers (secondary end-users)				
Inclusion criteria	
 
aged 18 years or older
 
be named by primary end-user as designated informal caregiver providing physical, emotional and/or social support for him or her
 
			
Both older adults and informal caregivers				

Inclusion criteria	•	written informed consent adequate functional, sensory and cognitive abilities to use the SENACA system
Exclusion criteria	•	does not have a stable address of residence inability to handle ICT-devices due to cognitive or functional disabilities

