#### 2.2.8 Data analysis

Explorative and descriptive data analyses will mainly be performed in this field-test study with a relatively small sample size.

First, descriptive analysis on usability will give a general overview of how users, both informal carers and patients, view SENACA before having used it. The findings will be compared with perceived usability after having experienced it for the whole intervention period (up to day 100). This will provide insights on practical implications on the design and introduction of SENACA. A qualitative analysis on break-offs and non-response further completes the findings by exploring the barriers and drivers of usage. In addition to that, the usage of the several components of SENACA will be compared regarding frequency and intensity to explore which aspects are more or less accepted by the user groups.

In a second step, the clinical and behavioural parameters and quality of life will be screened at baseline measurement. This initial description gives further insights into the characteristics of the sample. Changes in parameters over time will be explored to gain insight into the functionality of SENACA.

Overall, mean values will be compared on the basis of non-parametric tests to identify significant differences between groups. Even though the study does not meet the requirements of an experimental design, the ex-ante and ex post measurement allows monitoring changes of the observed variables. Bias due to non-observable errors may be possible.

Data from qualitative study parts (i.e. interview transcripts, content from open-ended questions or user forums) will be coded applying thematic analysis (Bradley, Curry & Devers, 2007) in order to categorize the data as well as to identify patterns leading to a nuanced evaluation of the usability of SENACA from a technological, educational and behaviour perspective. The qualitative analysis will be guided by taxonomies and frameworks on the subject of matter to be used as sensitizing concepts, for instance Michie et al. (2013) or Greenhalgh et al.(2015). Computer-aided qualitative data analysis (most likely MaxQDA®) will be used for coding and synthesising the findings.

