#### 11: Which of the following three chronic diseases do you have?

(Please tick each box that applies to you)

- Heart disease (chronic heart failure)
- Diabetes (Diabetes mellitus)
- Lung disease (chronic obstructive pulmonary disease)

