#### 12: Since how many years and months is this disease diagnosed?

(Please enter the exact number of years and months. If you don't remember the exact number please try to estimate. If you have ticked more than one box in E1, please refer to the disease that was diagnosed first)

Years	Months
13: Did you have hip and/or kr	nee replacement?
(Please tick one box only)	
L	L.
No	Yes

14: If you had hip or knee replacement, how many days passed by since that surgery? (Please enter the exact number of days. If you don't know the exact number please try to estimate)

Days |\_\_||\_\_|

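### Recovery after hip or knee replacement could appear as a SENACA gain in quality of life and activity, because the one-group analysis of change has no split by qualifying condition

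*Protocol*

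**What the plan says.** **Eligibility (section 2.2.2, Table 2).** Primary end-users must "receive medical care for one or more of the following chronic diseases in hospital settings and outpatient clinics". Heart failure, diabetes and COPD are listed, and a fourth entry follows: "Special Orthopaedic Co-Morbidity (SOCM, after elective hip or knee replacement, health status temporarily destabilized respectively challenged". As written, any one of the four is enough. The exclusion list rules out "major acute illness or surgery in past 3 months (except elective hip / knee surgery for patients with SOCM". No time since surgery, minimum or maximum, is given for the exempted patients.

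**Three conditions elsewhere.** Section 2.1 describes the field test as one in "older community-dwelling adults living with chronic conditions (i.e. diabetes, COPD, chronic heart failure) and informal caregivers". The Intervention section (2.2.3) also refers to three chronic conditions, although its activity component provides a modified programme after hip or knee replacement. Annex 7a, item 11, asks "Which of the following three chronic diseases do you have", with no orthopaedic box. Items 13 and 14 then ask about joint replacement: "If you had hip or knee replacement, how many days passed by since that surgery".

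**Design and outcomes.** Section 2.2.1 sets out "a pre-experimental design with a one-group pre-test post-test approach using a repeated post-test". Table 6 schedules EQ-5D-5L, health status, self-efficacy and physical activity at Days 0, 50 and 100. Annex 1 calls quality of life a main parameter, and the EQ-5D dimensions include mobility, self-care, usual activities and pain.

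**Analysis (section 2.2.8).** "Changes in parameters over time will be explored to gain insight into the functionality of SENACA". Means are to be compared between groups by non-parametric tests, but the groups are not defined and no split by qualifying condition is mentioned.

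**The concern.** In a design without a control group, change from baseline contains whatever would have happened anyway. For stable chronic disease that part may be modest and of uncertain sign. For people enrolled after joint replacement, in a state the protocol itself calls temporary, it is predictable and points towards improvement on the dimensions the EQ-5D and the walking questions measure. The surgery exclusion that keeps recovering patients out is lifted for this group only.

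If their change is averaged with everyone else's, part of the observed gain is post-operative recovery. Sections 2.1.1 and 2.2.1 say the results will help decide whether the platform merits further study and may feed estimates of its effect on care burden and cost. A favourable tilt therefore has consequences even in exploratory work.

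**Working it through.** The protocol states no figure to reproduce: no sample size, share of orthopaedic patients (SOCM in Table 2), expected recovery, SD or significance level. Everything numerical below is illustrative.

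**1. Size of the shift.** Assume SENACA has no effect and the other patients do not change. Let *f* be the SOCM share and *g* the natural recovery in that group between two visits. Then

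pooled mean change = *f* × *g* + (1 − *f*) × 0 = *f* × *g*.

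With assumed recovery in EQ-VAS points (scale 0 to 100):

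| Share *f* | *g* = 5 | *g* = 10 | *g* = 20 |
|---|---|---|---|
| 10% | 0.5 | 1.0 | 2.0 |
| 25% | 1.25 | 2.5 | 5.0 |
| 40% | 2.0 | 4.0 | 8.0 |

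**2. Chance of a spurious significant change.** Assumptions: normal changes with SD 1, *g* in units of that SD, a two-sided Wilcoxon signed-rank test at 0.05, and 2000 simulated studies per cell. The test and level are assumed; section 2.2.8 says only that tests are non-parametric.

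| N | Share (number) | *g* = 0.5 | *g* = 1.0 | *g* = 1.5 |
|---|---|---|---|---|
| 30 | 10% (3) | 5.8% | 6.6% | 8.4% |
| 30 | 25% (8, rounded) | 10.2% | 21.2% | 35.9% |
| 30 | 40% (12) | 17.4% | 44.4% | 72.2% |
| 60 | 10% (6) | 6.5% | 9.2% | 13.8% |
| 60 | 25% (15) | 13.3% | 36.2% | 62.8% |
| 60 | 40% (24) | 32.6% | 78.6% | 97.6% |
| 100 | 10% (10) | 6.0% | 14.1% | 20.7% |
| 100 | 25% (25) | 21.3% | 59.6% | 86.4% |
| 100 | 40% (40) | 47.5% | 95.4% | 100% |

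With no SOCM patients the rate is 4.4%, 4.4% and 4.8% for N = 30, 60 and 100, which is close to nominal.

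**3. Can these patients be separated?** Largely yes. No box ticked in item 11 of Annex 7a plus a positive item 13 points to someone who qualified through SOCM alone. A ticked box plus a positive item 13 indicates replacement alongside a chronic disease. Item 14 dates the operation. As reproduced in the text, its answer field has two digits and so holds up to 99 days, which covers the three months in which the waiver matters. Operations 100 or more days old do not fit the field. Clinicians also screen eligibility (section 2.2.2, Recruitment), so qualifying status need not rest on self-report alone.

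**4. Precision lost by separating.** With equal SDs, the standard error of mean change in the remaining patients grows by 1/√(1 − *f*): 1/√0.90 = 1.05, 1/√0.75 = 1.15 and 1/√0.60 = 1.29 for shares of 10%, 25% and 40%.

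**The case against.** **Pooling is inferred.** Section 2.2.8 does not say that all participants are averaged together, and an analysis plan not available here could stratify. That stands, so the bias is something that could occur. What the protocol does fix is the admission of these patients, the waiver without a time window, the single group, and the use of change over time to learn about the platform.

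**The protocol already disclaims strong inference.** Sections 2.2.1, 2.2.8 and 2.2.9 concede low validity, possible bias and the lack of a control group, and section 2.3 calls for a controlled trial. This limits the harm. It does not deal with a trend that is foreseeable, mostly in one direction, and confined to an identifiable subgroup.

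**These patients are an intended target group.** Section 2.2.3 plans a programme for them, so dropping them would discard wanted information. This also stands, and it favours separate reporting over exclusion. Removing only those who qualify through SOCM alone would also miss recent surgery alongside a chronic disease.

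**Readings that go too far.** A reader might compare the shift with the standardised effects of 0.18 and 0.20 cited in section 2.1 and conclude that recovery would reproduce the whole expected effect. Those figures concern clinical and continuous behavioural outcomes. For quality of life the protocol cites only a potential to improve, with no number, so there is no such benchmark. A reader might also infer that Annex 7a cannot identify these patients; step 3 shows that it largely can. Nor does the protocol show that the share is large: section 4.2.1 says Norway mainly targets heart failure.

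**Conclusion.** The point holds as a specific, avoidable source of favourable bias in EQ-5D-5L, VAS and physical activity. Self-efficacy may be affected too, since one item concerns pain and discomfort, but less directly.

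Its size is unknown. It equals share times natural recovery, and neither is given. Under the assumptions shown it is small at about a 10% share (false-positive rate 6% to 8% at N = 30, up to 21% at N = 100) and material at about 25% or more (10% to 86% across the scenarios at 25%). If most operations are well in the past at enrolment, little recovery remains and the bias shrinks; the protocol sets no window that would settle this.

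The conflict between four qualifying conditions in Table 2 and three elsewhere is real and needs no assumption. It leaves unclear whether SOCM qualifies alone or only as a co-morbidity. Under either reading the recovery trend lies within the analysed sample.

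This is a cheap and worthwhile improvement. It does not show that the study's findings would be invalid.

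**What to change.** 1. **Section 2.2.8:** report change in EQ-5D-5L, VAS, self-efficacy and physical activity separately for participants with recent joint replacement (SOCM alone or alongside a chronic disease) and for all others. Identify them from eligibility status and Annex 7a items 11, 13 and 14. Base statements about SENACA on the others, and do not attribute change in the SOCM stratum to the platform.
2. **Annex 7a, item 14:** record the date of surgery, or widen the field, so that recent and older operations can be told apart. This is a baseline item and should be settled before enrolment.
3. **Eligibility text:** reconcile Table 2 with sections 2.1 and 2.2.3 and Annex 7a item 11, stating whether SOCM qualifies alone or only as a co-morbidity.

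The cost is some wording and one questionnaire field, plus the loss of precision in step 4 of the working (standard error up by about 5% to 29% for shares of 10% to 40%) and a small, imprecise SOCM stratum. The remaining group is still uncontrolled, so the existing cautions in sections 2.2.1 and 2.2.9 continue to apply.
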